## **2. BACKGROUND**

Cardiogenic Shock complicating acute myocardial infarction (AMICS) is associated with significant mortality, with rates ranging from 40-60% (Kolte et al.; Wayangankar et al., 2016). To date, only early mechanical reperfusion has been shown to have a significant impact on mortality (Hochman et al., 2001). Hemodynamic support is commonly employed in patients with more severe forms of shock, but there remains considerable debate regarding the need, type of device, and timing of deployment. Moreover, approaches in the United States and Europe differ widely (Thiele et al., 2015; O'Neill et al., 2017), and randomized trials have yielded results that have failed to clarify the optimal strategies, resulting in broad clinical variation in treatment with both cost and outcome implications.

In addition to prompt mechanical reperfusion, the most commonly utilized adjunctive hemodynamic support include intra-aortic balloon counterpulsation (IABP), the micro-axial Impella 2.5, CP, and 5.0 systems, and extracorporeal membrane oxygenation (ECMO). Intra-aortic balloon counter-pulsation remains the most widely used device, although the hemodynamic effects are quite modest, with limited improvement in cardiac output despite diastolic augmentation and afterload reduction (Kern & Sato, 2016). In the IABP Shock II trial, 600 patients were randomized in open label fashion to IABP vs. no IABP in addition to mechanical reperfusion. A majority of patients received IABP after reperfusion, and there was no impact on mortality at 30 days or one year (Thiele et al., 2012). Based on the results of this trial, the European guidelines have been updated with a Class III recommendation for IABP in cardiogenic shock with the US with a Class IIb recommendation (ESC/EACTS, 2014; Levine et al., 2016).

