#### 4.4.2.1. Hypothesis 1.

##### Approach

To evaluate this hypothesis, we will use a discrete time survival analysis (DTSA) within the structural equation modeling (SEM) framework (Muthén & Masyn, 2005; Raykov, Gorelick, Zajacova, & Marcoulides, 2017). This approach offers substantively important extensions to conventional DTSA models (e.g., logistic regression) that more accurately reflects the complexity and interconnectedness of survival (i.e., event history modeling) processes (Masyn, 2014). This more general approach includes the ability to model unobserved population heterogeneity (frailty) in the event history process, latent variable predictors of event history (e.g., health-related quality of life) including possible mediators and moderators, recurring events, competing risks, parallel and sequential growth processes (i.e., between-person variability in within-person change over time), onset-to-growth models, parallel event history processes, measurement error on event occurrence, hazard risk set matching, handling multilevel data structures, and time-varying covariate effects (non-proportional hazard) among other advantages (Masyn, 2013, 2014). Figure 1 presents an exemplary DTSA within the context of SEM (simplified for ease of presentation). In this example, three binary indicators (1, event occurred; 0, event not occurred) corresponding to the  $j = 3$  proposed measurement occasions ( $e_j$ ). In this analysis the hazard probability for a given measurement occasion will be defined as the probability of mortality in that occasion, provided that patient is alive. The hazard probability will then be related to time-varying ( $w_j$ ) and time-invariant ( $x$ ) covariates through a logit link function to parameterize the effect of a particular covariate on the log hazard odds of mortality during a given time interval. We will then describe covariate effects in terms of a hazard odds ratio (hOR). For example, if clinical protocol is coded 1 for typical and 0 for being based on a shock severity score, were estimated to have a hOR of 2.0 at 30 days, we would note that the odds of mortality at 30 days for those without a shock severity protocol was twice the odds of mortality at 30 days for those with a shock severity protocol. This model can be written as:  $logit(Pr(e_j = 1)) = \alpha_j + \beta_j x + \gamma_j w_j$ , where  $\alpha_j$  is the log hazard odds (with all covariates set to 0),  $\beta_j$  is the difference in the log hazard odds and  $exp(\beta_j)$  is the hazard odds ratio (hOR) for a positive one unit difference in  $x$  (controlling for covariates  $w_j$ ), and  $\gamma_j$  represents a time-varying covariate effect for the difference in log hazard odds. The assessment of non-inferiority will be performed by comparing hazard odds ratio confidence intervals to the non-inferiority margin (Althunian, Boer, Groenwold, & Klungel, 2017). Specifically, since lower is better, non-inferiority will be concluded when the actual hazard ratio is less than the clinically acceptable ratio of 1.2.

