
### *Power*

With respect to the 30-day primary end point of death, we estimated that an overall sample size of 672 patients would provide 80% power (at a one-sided alpha level of 0.025) to show the noninferiority of a standardized clinical protocol that selects patients for MCS based on shock severity to a standard clinical protocol that does not differentiate based on shock severity assuming the proportion of subjects observed with the event (death) during the study is 39.7% for the control group and 41.3% for the treatment group (Thiele et al., 2005; Thiele et al., 2013). The power was computed for the case when the actual treatment group proportion is 31%. The test statistic used is the one-sided Z test (unpooled).

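### The stated 80% power rests on a 1.6-point limit and an assumed 8.7-point mortality benefit, not on the 1.2 hazard odds ratio rule; at equal mortality power is about 21%

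*Protocol*

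**What the plan says.** Section 4.4.2.1 (Hypothesis 1) settles the non-inferiority comparison in two paragraphs.

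- **Approach.** A discrete-time survival model with a logit link gives a hazard odds ratio, whose confidence interval is compared with the margin. Non-inferiority is concluded when the ratio is "less than the clinically acceptable ratio of 1.2". The paragraph calls this quantity a hazard odds ratio in one sentence and a hazard ratio in the next.
- **Power.** For 30-day death, "an overall sample size of 672 patients would provide 80% power" "at a one-sided alpha level of 0.025". The assumed proportion dying "is 39.7% for the control group and 41.3% for the treatment group". The paragraph then says: "The power was computed for the case when the actual treatment group proportion is 31" per cent. The test statistic is an unpooled one-sided Z test on proportions. The ratio of 1.2 does not appear.

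Section 4.1.1 makes 30-day all-cause mortality the primary outcome, and section 4.1 adopts 672 as the target accrual. Section 1.1 and the Expected results paragraph describe the hypothesis as non-inferiority and do not predict a large reduction in deaths.

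**The concern.** Three things in the Power paragraph do not fit the rest of the plan.

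1. The treatment group is given both 41.3% and 31%, and the text does not say which is the limit and which the expected truth.
2. If 41.3% is the limit, the tolerated excess over 39.7% is 1.6 points. That is a different margin from a ratio of 1.2.
3. The power is for a difference in proportions, whereas the planned decision uses a hazard odds ratio interval.

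A reader cannot tell how much excess mortality the study would accept. The 80% also depends on the shock-severity protocol being clearly better, and no source or reason is given for 31%. If selective use of support leaves mortality unchanged, which is what a non-inferiority hypothesis ordinarily supposes, the study will probably miss its criterion. That result could then be misread as evidence against deferral.

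**Working it through.** **Inputs.** From the Power paragraph: control 39.7%; treatment 41.3% and 31%; one-sided alpha 0.025; 672 in total; unpooled Z test. From the Approach paragraph: ratio margin 1.2. Assumed: equal groups of 336, because the protocol gives only an overall number.

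**Step 1: reproduce the plan's figure.** Take 41.3% as the limit and 31% as the true rate.

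n per group = (1.960 + 0.842)² × [0.397×0.603 + 0.31×0.69] / (0.413 − 0.31)²
= 7.849 × (0.2394 + 0.2139) / 0.103² = 335.4, so 336 per group and 672 in total.

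Power at 336 per group: SE = √[(0.2394 + 0.2139)/336] = 0.03673. Then Φ(0.103/0.03673 − 1.960) = Φ(0.844) = 0.801.

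Other readings of the paragraph do not return 80%: one-sided 0.05 gives 87.7%, one-sided 0.0125 gives 71.3%, 2:1 allocation gives 75 to 76%, and a zero margin gives 66%.

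**Step 2: compare the two margins.**

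- Power paragraph: 41.3% against 39.7% is +1.6 points, a risk ratio of 0.413/0.397 = 1.040, and an odds ratio of (0.413/0.587)/(0.397/0.603) = 1.069.
- Decision rule, as an odds ratio: the control odds are 0.6584, and 1.2 × 0.6584 = 0.790. The limit is 0.790/1.790 = 44.1%, or +4.4 points.
- Decision rule, as a hazard ratio: 1 − 0.603^1.2 = 45.5%, or +5.8 points.
- Decision rule, as a risk ratio: 1.2 × 39.7% = 47.6%, or +7.9 points.

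On the odds scale the decision rule tolerates 4.4/1.6, or about 2.8 times, the excess used for the sample size.

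**Step 3: power of each test at 336 per group.**

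Odds ratio test: Φ[(ln 1.2 − ln OR)/SE − 1.960], with SE = √[1/(336·pC(1−pC)) + 1/(336·pT(1−pT))].
Example at equality: SE = 0.1577, and 0.1823/0.1577 − 1.960 = −0.804, so power is 0.211.

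Difference test: Φ[(0.016 − (pT − pC))/SE − 1.960].
Example at equality: SE = 0.03775, and 0.016/0.03775 − 1.960 = −1.536, so power is 0.062.

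| True mortality, new protocol | Odds ratio 1.2 | 1.6-point limit |
|---|---|---|
| 31% | 93.5% | 80.1% |
| 35% | 67.0% | 39.4% |
| 39.7% (equal) | 21.1% | 6.2% |
| 41.3% | 11.1% | 2.5% |

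Simulation with 400,000 replicates agrees: at equality 20.3% and 6.2%; at 31%, 93.5% and 80.1%.

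**Step 4: what success requires.** On the odds ratio of 1.2, 80% power needs true mortality of about 33.5% or lower. With mortality near 39.7% in both groups, the upper confidence limit falls below 1.2 only if the observed odds ratio is at most exp(0.1823 − 1.960 × 0.1577) = 0.88.

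**Step 5: size needed for 80% power at equality.** On the odds ratio of 1.2: 2 × 7.849/(0.2394 × 0.1823²), or about 1,973 per group. On the 1.6-point limit: 2 × 0.2394 × 7.849/0.016², or about 14,680 per group.

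**Step 6: sensitivity at equal mortality.** Reading 1.2 as a hazard ratio gives about 32% (Schoenfeld, 672 × 0.397 = about 267 deaths). Reading it as a risk ratio gives about 48%. With 2:1 allocation, the odds ratio test has 19% and the 1.6-point test 5.9%.

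**The case against.** The strongest reply is that the study is not undersized on its own terms. At the stated 31%, the 1.2 odds ratio test has 93.5% power, so 80% understates it. The 31% is disclosed, assuming some benefit in a non-inferiority calculation is not an error in itself, and the Rationale gives a direction for it: fewer device complications in milder shock. This stands as far as it goes. It makes adequacy depend entirely on an 8.7-point benefit for which the document gives no support, and it does not make 80% the power of the planned test.

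Four further caveats are fair.

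- The 21% is for the odds ratio reading, which gives the lowest power of the three scales. The range at equality is 21% to 48%, still far below 80%.
- Equal allocation is inferred because it returns 672. A registry does not fix its group sizes.
- The figures above are unadjusted. The planned model may carry covariates and a site term, which would change them somewhat.
- The Background says the condition "is associated with significant mortality, with rates ranging from 40-60" per cent, and 31% lies below that. This carries little weight: the control rate of 39.7% is also just below the range, and the eligibility criteria select patients.

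The fallback under Potential problems and alternatives uses a z statistic on Kaplan–Meier failure rates, which is closer to the test that was powered. It states no margin, so it does not settle the mismatch.

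**Conclusion.** The concern holds and needs correcting. The stated 80% belongs to a test of a 1.6-point limit with a true 8.7-point benefit, while the protocol will decide on a ratio of 1.2. That 41.3% served as the limit is an inference, but it reproduces both 672 and 80%. For the rule as modelled (odds ratio 1.2, 336 per group, control 39.7%, one-sided 0.025, unadjusted), power runs from about 94% at a true 31% to about 21% at equal mortality. If deferral has no effect on mortality, the study misses its criterion about four times in five. No reading of 1.2 brings power at equality above about 48%.

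**What to change.** Use one margin in both paragraphs and name its scale, choosing between hazard odds ratio and hazard ratio.

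- **If the hazard odds ratio of 1.2 stays:** replace the Power paragraph with the power of that test at the planned group sizes over a range of true rates. At 336 per group this is about 94% at 31%, 67% at 35% and 21% at 39.7%. Label the figures as unadjusted approximations with equal groups, or replace them with a simulation of the planned model.
- **If 41.3% was meant as the limit:** say so and change the decision margin to 1.6 points (hazard odds ratio about 1.07). Power at equal mortality is then about 6%.

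In either case, state which figure is the limit under the null and which is the assumed true rate, justify the 31%, and say openly what benefit the power claim presumes. Recompute if the comparator or the group sizes change.

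The cost is one rewritten paragraph, plus one edit to the decision rule under the second option, and no added patients. The stated power will look less favourable. The rewrite does not raise power at equal mortality; it lets readers interpret a failure to show non-inferiority correctly.

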### *Expected results*

We expect a standardized clinical protocol that selects patients for MCS based on shock severity, will be non-inferior with respect to 1 month and 1 year mortality compared to standard clinical protocols that do not differentiate based on shock severity in adult patients following an initial diagnosis of acute myocardial infarction complicated by cardiogenic shock (AMICS).

### *Potential problems and alternatives*

The issue of multiple testing that is involved in evaluating the p-values associated with a large set of covariates, is not addressed through the use of SEM. To address this concern, we will use the Benjamini–Hochberg (BH) procedure that is based on the false discovery rate concept, and has been shown to be more powerful than conventional multiple testing procedures (Benjamini & Hochberg, 1995; Benjamini & Yekutieli, 2001; Raykov, Lichtenberg, & Paulson, 2012). The inclusion of time-dependent covariates introduces reciprocal causation (Singer & Willett, 2003). We will address this issue by modeling covariate effects with a time-lag (Brown, 2012; Little, 2013). Model comparisons based on the Wald statistic test (dividing a parameter estimate by its standard error), may be influenced by non-normal concentration distributions (Little, 2013). To address this, we will use the adjusted likelihood ratio test statistic (i.e., Chi-Square Difference Test) using the log likelihood values and scaling correction factors obtained with the “MLR” estimator in Mplus, the default maximum likelihood estimator for binary and ordinal outcomes (Wang & Wang, 2012). In the event of unforeseen problems related to the proposed models, we will simplify our approach by modeling single-occurrence events in discrete-time with observed predictors using a multivariate logistic regression to model conditional model-estimated hazard probabilities and corresponding survival probabilities (Masyn, 2014; Muthén & Masyn, 2005). In this case, noninferiority will be calculated with the use of the Com–Nougue approach to estimating the z statistic for the Kaplan–Meier failure rates, with standard errors estimated by means of Greenwood’s formula (Com-Nougue, Rodary, & Patte, 1993).

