**Confidential**

The information provided in this document is strictly confidential and is intended solely for the guidance of the clinical investigation. Reproduction or disclosure of this document whether in part or in full to parties not associated with the clinical investigation, or its use for any other purpose, without the prior written consent of the Principal Investigator is not permitted.

Throughout this document, symbols indicating proprietary names (®, TM) are not displayed. Hence, the appearance of product names without these symbols does not imply that these names are not protected.

*Version 2 / Date 05/08/2020*

PROTOCOL SUMMARY	
Study Title	Carolinas Cardiogenic Shock Initiative
Study Design	This is a case series and prospective patient registry
Study Objectives	To determine if deferred or delayed implantation of Impella device based on shock severity index is non-inferior with respect to 1 month and 1 year mortality compared to standard clinical protocols that do not differentiate based on shock severity in adult patients following an initial diagnosis of acute myocardial infarction complicated by cardiogenic shock (AMICS).
Study Population	The registry will include all eligible subjects from approximately 5/1/2019 until 4/30/2024, at participating sites.
Study Procedures	Adult patients with a diagnosis of AMICS will have their clinically available data contribute to the project registry. Patients who meet criteria for inclusion into the registry will have their chart reviewed periodically for the purposes of the registry, for proof of survival at one month and one year post-admission. Social Security Death Index (SSDI) data will be used to determine mortality at one month and one year if unable to confirm using the electronic health record. Patient clinical data will be pulled from the medical record and entered or migrated into a database for comparison and analysis. All data collected for the study will originate in the medical record from clinically available information, from a national death database, or from other publically available data sources.

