## 4. INVESTIGATIONAL PLAN

### 4.1 Overall Study Design

The Carolinas Cardiogenic Shock Initiative is a clinical pathway and process improvement protocol already agreed upon by participating sites, to improve care by using a standardized algorithm to treat patients with AMI and CS. This prospective registry will capture data from this protocol as a multi-site research project in parallel with this standardized non-research clinic workflow protocol. Participating providers will follow the clinical protocol as standard of care for AMICS patients, as clinically appropriate. Patients who have been admitted and diagnosed with AMICS and meet all eligibility criteria will have their data entered in this registry.

All eligible patients will be entered into the registry and follow-up via the EMR and/or SSDI will occur at 30 days and one year to assess mortality. No additional provider appointments or further testing will be required as a part of this Registry, other than what each provider feels is medically necessary and indicated as a part of the patients' care plan.

Treatment decisions and timing will follow an approved clinical protocol and algorithm (see Appendix A) based on shock severity classification. The research team at each site will capture data generated during standard of care lab tests and clinical procedures, as well as data collected during clinical visits from eligible patients. Our target accrual is approximately 672 patients, cumulative across all participating sites.

Many of the patient specific outcomes and variables of interest for this study, are already submitted to the National Cardiovascular Data Registry (NCDR). Some additional data elements, as described in Appendix C, will also be captured. There are no benefits in participation other than the scientific knowledge gained, and the only alternative to participation is not participating.

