#### 4.1.1 Primary Outcome Variable

The primary outcome variable will be 30-day all cause mortality.

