### 4.4 Statistical Analysis

**4.4.1. Exploratory analysis.** Variable distributions will be examined using summary measures, tables, and graphics, such as histograms and scatter plots, where appropriate. Variables will initially be used as they were obtained; however, transformation may be

necessary or prove more informative. For example, continuous variables may be categorized, using common category boundaries found in the literature or based on percentiles of the variable distribution, in order to stratify the data. Student's t-test or the Wilcoxon rank-sum and chi-square statistics will be used to examine simple associations. For event history outcomes, we will primarily rely on survival analysis (i.e., event history modeling) to investigate if and when the event has occurred (Singer & Willett, 1993). For this study, the time scale for mortality will be recorded in discrete time intervals (i.e., baseline, one month, one year); therefore, the underlying continuous time-to-event process will be modeled using discrete time.

A major consideration will be the nested organization of the data. Patients (level-1) are nested within sites (level-2). When hierarchical data are analyzed without regard to the interdependence of the data type-I error rates are inflated (aggregation) or deflated (disaggregation) resulting in incorrect significance tests and invalid conclusions (Hox, 2002). While multilevel modeling methods explicitly account for the nested structure of data, this approach is not feasible because we do not have sufficient number of sites to treat these effects as random (Hox & Roberts, 2010; Roberts, Monaco, Stovall, & Foster, 2011). Therefore, each site will be evaluated for differences in multiple group analyses. If the site differences are trivial, we will collapse the data across sites (Little, 2013). Non-trivial differences will require a grouping variable for site in subsequent analyses.

**4.4.2. Analytic strategy.** Insights gained from the exploratory data analysis will then be used to fit appropriate statistical models to the data. Within the context of survival analyses, we will begin by modeling the unconditional model (no covariates) in order to establish a baseline model. Next, we will add covariates with time-varying (nonproportional hazard odds) effects. Using model constraints, we will then fit a proportional hazard odds model and compare. Finally, we will probe for hypothesized effects.

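### The fallback non-inferiority verdict comes from a Kaplan–Meier comparison with no covariate adjustment, although the registry is not randomised and an adjusted model is fitted in the same step

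*Protocol*

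**What the plan says.** The Protocol Summary describes the design: "This is a case series and prospective patient registry". Section 4.1 adds: "Treatment decisions and timing will follow an approved clinical protocol and algorithm", with shock severity as the basis. Nothing is allocated at random. Section 4.1.1 fixes the endpoint: "The primary outcome variable will be 30-day all cause mortality".

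The main rule is in section 4.4.2.1, Approach. A discrete-time survival model with time-invariant and time-varying covariates yields an hOR for clinical protocol. The rule is: "The assessment of non-inferiority will be performed by comparing hazard odds ratio confidence intervals to the non-inferiority margin". The margin follows: "non-inferiority will be concluded when the actual hazard ratio is less than the clinically acceptable ratio of 1.2".

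The fallback is in the same section, under Potential problems and alternatives. If the proposed models meet difficulties that were not anticipated, a discrete-time logistic regression with observed predictors replaces them. For that situation the text says "noninferiority will be calculated with the use of the Com–Nougue approach", applied to Kaplan–Meier failure rates with standard errors from Greenwood's formula. It mentions no covariates, weighting, matching or stratification for this test.

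**The concern.** The main rule and the fallback answer the same primary question, but only the main rule controls for differences between the patient groups. The fallback fits a model that could supply an adjusted estimate, then takes the decision from a quantity that ignores it. Kaplan–Meier rates and Greenwood variances are computed from observed counts and contain no covariates.

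The comparison is between patients managed under a severity-based protocol and patients managed under protocols that do not differentiate by severity. Without randomisation, nothing makes the share of severe cases equal in the two groups. Shock severity is the central prognostic factor of this study, so an imbalance in it goes straight into a crude difference in 30-day mortality. At stake is the error rate of the non-inferiority conclusion whenever the fallback is used.

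**Working it through.** **1. The plan's own figure.** Section 4.4.2.1, Power, gives 672 patients in total, 80% power, one-sided alpha 0.025, control mortality 39.7%, a treatment figure of 41.3%, an actual treatment mortality of 31%, and an unpooled Z test. Equal group sizes are assumed here, because the text states no ratio. Reading 41.3% as the limit of the test:

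n per group = [0.397 × 0.603 + 0.31 × 0.69] × (1.960 + 0.842)² / (0.413 − 0.31)² = 335.4, so 336 per group and 672 in total.

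The figure reproduces, and 336 per group is used below.

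**2. What the fallback test is at 30 days.** Section 4.4.1 says "the time scale for mortality will be recorded in discrete time intervals", namely baseline, one month and one year. With no censoring before 30 days, the Kaplan–Meier failure rate is deaths divided by patients, and Greenwood's variance is p(1 − p)/n. The z statistic on a difference in failure rates is then the unpooled two-proportion Z test: a crude comparison.

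**3. Bias from case-mix (assumed mortality).** The documents give no mortality by severity. Assume 50% in severe and 30% in milder shock. A control rate of 39.7% then corresponds to a severe share of (0.397 − 0.30)/0.20 = 48.5%, so the assumption is compatible with the plan's control figure.

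Bias in the crude difference = imbalance in severe share × (0.50 − 0.30):
- 5 points: 0.05 × 0.20 = 1.0 point
- 10 points: 0.10 × 0.20 = 2.0 points

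**4. Effect on type I error.** Translate the stated margin of 1.2, as an odds ratio, at 39.7%: odds 0.397/0.603 × 1.2 = 0.790, giving a limit of 0.790/1.790 = 44.1%, or +4.4 points. Put the true difference exactly at that limit, and let the severity-based group have fewer severe patients, so that its expected crude rate is 44.1% minus the bias.

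SE = √{[0.397 × 0.603 + p(1 − p)]/336}, about 3.8 points. Type I error = Φ(bias/SE − 1.96).

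| Mortality, severe / milder (assumed) | Imbalance favouring the new protocol | Bias | Bias/SE | One-sided type I error |
|---|---|---|---|---|
| any | 0 | 0 | 0 | 2.5% |
| 50% / 30% | 5 points | 1 point | 0.26 | 4.5% |
| 50% / 30% | 10 points | 2 points | 0.53 | 7.6% |
| 60% / 20% | 10 points | 4 points | 1.06 | 18.4% |
| 60% / 20% | 20 points | 8 points | 2.14 | 57% |

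The result hardly depends on the margin: with a limit of +1.6 points instead, the 2- and 4-point biases give 7.6% and 18.6%.

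**5. The opposite direction.** If the new-protocol group has more severe patients, the sign reverses. A 1-point bias gives Φ(−0.26 − 1.96) = 1.3%, and a 2-point bias gives Φ(−0.53 − 1.96) = 0.6%. The test becomes conservative and loses power.

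**The case against.** **It is only a contingency.** The main rule stays covariate-based, and in the fallback the logistic model would still give an adjusted hOR to set beside the crude result. This is true and limits the reach of the point. But the plan assigns the decision to the crude test, so if the two disagree, the crude test prevails.

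**The adjusted probabilities might be meant to feed the z statistic.** The wording does not say so, and Greenwood's formula is not the variance of model-predicted risks. On that reading the named standard error would be wrong, so the sentence needs correction either way.

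A reader might also infer stronger points that the protocol does not support:
- **That case-mix would decide the verdict.** Biases of 1 to 2 points are 0.26 to 0.53 of a standard error. That is a real inflation but not a decisive one, and it harms error control only in one direction.
- **That the margin is 1.6 points (41.3% less 39.7%), so that a 2-point bias exceeds it.** The power paragraph never calls this a margin, and it does not match 1.2, which is +4.4 points as an odds ratio at 39.7%. The mismatch is a separate matter.
- **That the fallback moves to a scale for which the margin is missing.** Whether the cited method takes a ratio or a difference margin depends on a source not at hand, and such detail may sit in the statistical analysis plan.
- **That Kaplan–Meier adds nothing.** At 30 days without censoring it reduces to simple proportions. The hypothesis also covers one-year mortality, and the Missing Data section allows for right censoring, where such an estimator can be useful.
- **That a better fallback would cure the data-dependent trigger.** Any switch prompted by model failure is made after fitting has begun. Naming the alternative in advance is the usual safeguard, and the fix below leaves the trigger as it is.

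**Conclusion.** The point stands in a limited form. When the fallback is used, the plan takes the primary non-inferiority verdict from a comparison with no covariate adjustment, in a non-randomised registry, although an adjusted model is fitted in the same step. Under the assumed 50% and 30% mortality, with 336 per group and an imbalance of 5 to 10 points favouring the new protocol, one-sided type I error is about 4.5% to 7.6% instead of 2.5%. With 60% and 20% and a 10- to 20-point imbalance it is about 18% to 57%.

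These sizes rest on assumed mortality by severity, assumed imbalance, an equal split and no censoring before 30 days. The direction of any imbalance cannot be known from the protocol. That the fallback test carries no adjustment does not depend on these assumptions.

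**What to change.** In section 4.4.2.1, Potential problems and alternatives, replace the sentence on the Kaplan–Meier z statistic. Take the fallback verdict from the adjusted discrete-time logistic model named just before it: conclude non-inferiority if the upper confidence limit of the 30-day hOR is below 1.2. This keeps the scale, margin and adjustment of the main rule. State that the hOR is the severity-based protocol relative to the standard one, because the worked example under Approach codes the groups the other way round.

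Keep the Kaplan–Meier/Greenwood comparison as unadjusted description only. If standardised risks from the logistic model are preferred, give them a bootstrap or delta-method interval and state a margin on that scale.

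The cost is about one sentence, with no new data and no new model. Under the plan's own 39.7% and 31%, the sample size is enough in an approximate check without covariates. The log odds ratio is ln(0.449/0.658) = −0.382, its SE with 336 per group is 0.162, and power against 1.2 is Φ[(0.182 + 0.382)/0.162 − 1.96], about 94%. If true mortality were equal at 39.7%, the SE would be 0.158 and power Φ(0.182/0.158 − 1.96), about 21%. The adequacy therefore rests on the planned benefit.
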